Conducted by: National Institute of Allergy and Infectious Diseases and

National Institutes of Health Clinical Center

Principal Investigator: [name], MPH

Sample Size: N = 50; 25 subjects in intermittent caloric restriction arm,

25 subjects in lifestyle modification standard of care arm

Accrual Ceiling: 100

Study Population: Human immunodeficiency virus (HIV)-infected adults aged

18 to 65 with a body mass index ≥30 kg/m² (obese) and at least one feature of the metabolic syndrome (increased waist

circumference, systolic hypertension, dyslipidemia)

Accrual Period: 3 years

Study Design: Randomized study with 2 parallel arms

Study Duration: 5 years (estimated start date of February 2018; end date

January 2023

Intervention Description: Prospective randomized 12-week diet intervention study;

2 days of intermittent caloric restriction (fasting) per week vs

standard of care.

Primary Objective: To evaluate the effects of 12 weeks of intermittent caloric

restriction 2 days per week on weight and insulin sensitivity

in obese HIV-infected individuals with features of the

metabolic syndrome

Primary Endpoint: Changes in weight and insulin sensitivity as measured by

homeostatic model assessment of insulin resistance

(HOMA-IR) between baseline and week 12

Précis

The high prevalence of obesity coupled with chronic inflammation and immune activation places human immunodeficiency virus (HIV)-infected individuals at increased risk for metabolic complications, emphasizing the need for more aggressive management of obesity and related comorbidities in the aging HIV-infected population. The most effective treatment for obesity and metabolic syndrome is lifestyle modification, usually with a combination of caloric restriction and increased exercise. Intermittent caloric restriction (ICR) or intermittent fasting simplifies caloric restriction by severely limiting calories only a few days per week and allowing ad lib diet on the other days. Weight loss benefits are similar to those seen with conventional diets; however, data suggest possible added health benefits from intermittent fasting.

We propose to study the benefits of a 2-5 ICR strategy on weight, insulin resistance, and cardiovascular disease markers in obese HIV-infected adults with features of the metabolic syndrome. In a prospective pilot study, 50 HIV-infected adults will be randomized 1:1 to ICR or standard-of-care instruction of healthy diet and lifestyle for a 12-week intervention period. We hypothesize that ICR (2 days per week) will be an effective and acceptable diet strategy that will result in significant weight reduction, improvements in insulin sensitivity, and related metabolic parameters.

1 Background Information and Scientific Rationale

1.1 Background Information

Since the introduction of antiretroviral therapy (ART), human immunodeficiency virus (HIV)-infected individuals have lower morbidity from opportunistic infections and increased life expectancy. However, as HIV-infected individuals live longer, the prevalence of comorbid conditions, including obesity and metabolic syndrome, is increasing.

In HIV-negative populations, obesity, alone or as part of the metabolic syndrome, is associated with increased risk of diabetes, hypertension, cardiovascular disease, and dementia. HIV infection and ART are independent risk factors for comorbidities, including central obesity, insulin resistance, diabetes, atherosclerosis, and dementia. Coupled with HIV-related inflammation and immune activation, the high prevalence of obesity places HIV-infected individuals at increased risk for metabolic complications and highlights the need for more aggressive management of obesity and related comorbidities in the aging HIV-infected population.

Both treated HIV infection and excess adipose tissue promote similar changes in immune activation that are implicated in the development of a range of chronic diseases; however, at present, there are little data on whether the effects of treated HIV and excess adiposity are synergistic or additive.

1.1.1 Weight Gain and Obesity in HIV

Many HIV-infected individuals starting ART experience a significant gain in weight, regardless of weight at the time of antiretroviral initiation [1-4]. With the move towards earlier start of ART, an increasing number of HIV-infected individuals will initiate ART with normal or excess body weight.

In a cohort of 175 HIV-infected ART-naïve adults with advanced HIV/acquired immunodeficiency syndrome (AIDS) (cluster of differentiation 4 [CD4] < 100 cell/mm³) followed in the NIAID/Clinical Center intramural HIV/AIDS outpatient clinic from 2010 to 2012, 32% were overweight or obese at the time of ART initiation; rates nearly doubled after one year of therapy, with 63% of individuals overweight or obese. We have recently shown that this weight gain is accompanied by metabolic complications that include a high prevalence of non-alcoholic steatohepatitis and cardiac dysfunction [5, 6].

Our observations are mirrored in other cohorts. In one large US outpatient cohort, nearly half of HIV-infected individuals were overweight or obese at the time of ART initiation and weight increased to a higher body mass index (BMI) category within 2 years of initiation in 20% [4]. In a Veterans' Affairs cohort, HIV-positive veterans gained significantly more weight one year after initiation of ART compared to age and sex-matched HIV-negative controls [7].

Not surprisingly, these weight changes translate to increased risk of metabolic complications. In the Veterans' Affairs cohort, weight gain was more strongly associated with increased risk of incident diabetes mellitus in HIV-positive individuals (10% more risk per 5-lb gain) compared with HIV-negative individuals (6% more risk per 5-lb gain).

In the multi-cohort Data Collection on Adverse Events (AEs) of Anti-HIV Drugs (D:A:D) study, weight gain in the first year after initiation of ART is associated with an increased risk of cardiovascular disease and diabetes [8]. Taken together, these data suggest that weight gain in HIV-infected adults has significant implications for long-term health outcomes.

Treatment

For both HIV-infected and non-HIV-infected individuals, the most effective treatment for obesity and metabolic syndrome is lifestyle modification, usually a combination of caloric restriction and increased exercise [9-11]. A few small studies looking at lifestyle modification in HIV have shown improvement in dyslipidemia, waist circumference, systolic blood pressure, and hemoglobin (Hgb) A1C levels with dietary or exercise interventions [12-14].

Beyond lifestyle modification, subsequent approaches include drug therapy and, in obese individuals with serious medical comorbidities, bariatric surgery. In HIV-infected adults with lipodystrophy, a number of potential therapies have been studied unsuccessfully, including changes in ART, use of insulin-sensitizing agents, hormonal therapies such as growth hormone, growth hormone–releasing hormone, testosterone, and HMG-CoA reductase inhibitors (statins) [15].

1.1.2 Caloric Restriction and Intermittent Fasting

Caloric restriction without malnutrition slows aging and increases lifespan in a variety of organisms, including worms, spiders, fish, and rodents. In rhesus monkeys, caloric restriction reduces the incidence of type 2 diabetes mellitus, cardiovascular disease, and cancer, and may increase longevity [16, 17]. Caloric restriction also protects monkeys against age-related muscle loss and grey matter volume shrinkage in several key subcortical regions [18].

Studies in humans have confirmed the benefits of sustained calorie restriction; however, controversy exists related to subject selection, diet composition, and the duration of restriction required for beneficial effects to emerge. In one trial, adults following a calorie-restricted diet for 6 years (n=18) had improved body composition, lipid profile, blood pressure, insulin sensitivity, C-reactive protein (CRP), and carotid artery intimamedia thickness compared to adults on an unrestricted diet (n=18) [19]. In a 6-month, randomized study of calorie restriction with or without exercise in overweight, non-obese adults (n=48), caloric restriction reduced metabolic rate independently of weight change and improved insulin sensitivity [20].

One hypothesis to explain the beneficial, anti-aging effects of calorie restriction is reduced energy expenditure with a consequent reduction in the production of reactive oxygen species (ROS) [21]. However, other metabolic effects associated with calorie restriction, including alterations in insulin sensitivity and signaling, neuroendocrine function, stress response, or a combination of these, may also contribute to the benefits [22].

ICR or intermittent fasting simplifies caloric restriction by severely limiting calories only a few days per week and allowing ad lib diet on the other days. Benefits are similar to those seen with caloric restriction (where daily caloric intake is reduced but meal

frequency is maintained). However, data from animal models and a few human studies suggest possible added benefits from intermittent fasting [23-25]. For example, in mouse studies performed by [name] and his colleagues, intermittent fasting is superior to continuous calorie restriction for improving insulin sensitivity, cardiovascular function, and for protecting neurons in animal models of Alzheimer's and Parkinson's diseases [25-28].

In a cohort of overweight adults with asthma, [name] group has shown that 8 weeks of alternate day caloric restriction decreased weight (\sim -8% of baseline body weight), reduced peripheral insulin resistance, reduced plasma inflammatory markers, including decreased tumor necrosis factor- α (TNF- α , Figure 1), and decreased levels of ROS-induced 8-isoprostane, protein carbonyl, and nitrotyrosine (Figure 2) [29].

[figure not shown]

Figure 1.

The effect of alternate day calorie restriction (CR) on serum TNF- α . By the 8-week time point, concentrations were greatly reduced regardless of assessment on ad libitum (AL) or restricted (CR) days.

[figure not shown]

Figure 2.

The effect of alternate day calorie restriction (CR) on serum levels of nitrotyrosine. By the 8-week time point, levels decreased regardless of assessment on ad libitum (AL) or restricted (CR) days.

In a 6-month study comparing intermittent with continuous caloric restriction (CCR) in overweight women, both regimens produced comparable weight loss (average loss of 6 kg) and reductions in total and low-density lipoprotein cholesterol, triglycerides, blood pressure, and CRP [30]. ICR resulted in significantly greater reduction in visceral fat and improvement in insulin sensitivity relative to continuous restriction and was easier for subjects to maintain. Several short-term studies have shown similar benefits and confirmed the safety of the approach, with no evidence of overconsumption on unrestricted diet days [31-35].

The mechanisms underlying the benefits of intermittent fasting are beginning to be established. Fasting mice have higher levels of brain-derived neurotrophic factor (BDNF), a protein that regulates synaptic plasticity, neurogenesis, and neuronal survival in the brain. Recent work by [name] and others has identified a widespread role for BDNF in regulation of energy homeostasis. BDNF influences multiple cell types in the body that are involved in glucose metabolism, including pancreatic β cells (increased insulin production), hepatocytes (decreased glucose production), and skeletal muscle (increased insulin sensitivity) [36-38]. Fasting also appears to increase autophagy, a mechanism by which cells can eliminate damaged molecules, including ones that have been previously associated with Alzheimer's, Parkinson's, and other neurological diseases. Moreover, in contrast to caloric restriction without fasting, intermittent fasting results in depletion of liver glycogen stores, release of fatty acids from adipose cells, and metabolism of the fatty acids to generate ketone bodies. Ketone bodies may mediate some of the beneficial effects of intermittent fasting on the brain and cardiovascular systems [39], and recent findings suggest that ketones can protect neurons in experimental models relevant to HIV-associated neurocognitive disorders [40].

1.2 Rationale

With the rising prevalence of overweight and obesity in HIV-infected individuals, strategies to prevent and reverse weight-related comorbidities are needed. Caloric restriction can reduce weight and improve insulin resistance; however, daily caloric restriction is difficult to maintain long-term. Limited data suggest ICR may be easier to achieve and is superior to CCR for improving insulin sensitivity, cardiovascular function, and neuroprotection.

This study seeks to evaluate the tolerability and effects of ICR on body weight, insulin sensitivity, cardiovascular disease risk, and cognitive function. Additionally, we aim to characterize the effects on body composition, hepatic steatosis, resting energy expenditure (REE), plasma biomarkers of inflammation, immune activation, and metabolism. The results of this study may provide valuable information on the interactions between obesity and HIV-related inflammation and associated risk of non-AIDS disorders, and educate the design of future studies of obesity and associated comorbidities in HIV-infected populations.

2 Study Objectives

2.1 Primary Objectives

 To evaluate the effects of 12 weeks of ICR 2 days per week on weight and insulin sensitivity in obese HIV-infected individuals with features of the metabolic syndrome.

2.2 Secondary Objectives

- To evaluate the effects of ICR on body composition, including visceral adiposity and hepatic steatosis, lipids levels, metabolic biomarkers, biomarkers of inflammation and immune activation, and mood.
- To assess the tolerability of ICR.

3 Study Design

3.1 Description of the Study Design

After completing screening procedures and establishing eligibility, all subjects will receive standard-of-care recommendations for healthy diet and lifestyle and will be randomized 1:1 to either 2 days of ICR per week with 5 days of ad lib eating (2-5 ICR) or no additional intervention (see below).

Standard of Care (n=25)	2-5 ICR (n=25)
 AHA dietary counselling Lifestyle and physical activity counselling Pedometer and instructions for use 	 AHA dietary counselling Lifestyle and physical activity counselling Pedometer and instructions for use
	ICR guidelines and instructionsSupplemental beverages for ICR days

All subjects will receive dietary counseling consistent with the American Heart Association (AHA) diet recommendations. Like the standard-of-care arm, the 2-5 ICR subjects will implement the AHA diet 5 days per week; however, on 2 days per week will consume approximately 25% of their estimated daily caloric needs in the form of supplemental beverages or small meals. Assessments will occur prior to randomization and at 1, 4, 8, and 12 weeks. All subjects will then complete a follow-up visit to assess changes in weight and metabolic parameters 12 weeks after the intervention period is complete.

3.1.1 Study Endpoints

3.1.1.1 Primary Endpoint

Change in weight and insulin sensitivity as measured by homeostatic model assessment of insulin resistance (HOMA-IR) between baseline and week 12.

3.1.1.2 Secondary Endpoints

- 1. Tolerance and adherence to diet assignment
- 2. Change in the following after 12 weeks of caloric restriction:
 - Visceral adiposity as measured by dual x-ray absorptiometry (DXA) and waist circumference
 - Fat and lean mass as measured by DXA
 - Hepatic steatosis and liver stiffness as measured by transient elastography
 - Lipid profile
 - REE as measured by indirect calorimetry
 - Serum biomarkers of inflammation (eg, CRP, TNF-alpha) and immune activation

4 Study Population

4.1 Recruitment Plan

Subjects will be recruited from existing National Institutes of Health (NIH) cohorts as well as HIV care clinics in the greater Washington, DC area. In addition, we will use the OP8 Clinic recruitment strategies that are in place and include a full-time subject recruiter and community-based outreach within local area clinics specializing in HIV care.

4.2 Subject Inclusion Criteria

- 1. Aged 18 to 65 years
- 2. HIV RNA level ≤200 copies/mL for ≥1 year (1 measure ≥200 allowed if also <500 and preceded and followed by one or more undetectable values)
- 3. CD4 >200 cells/mL and no active opportunistic infection or malignancy
- 4. BMI ≥30 kg/m²
- One or more components of the metabolic syndrome as defined in the table below.

Table 1. ATPIII Clinical Identification of the Metabolic Syndrome [41]

Risk Factor	Defining Level		
Waist circumference			
Men	>102 cm		
Women	>88 cm		
Triglycerides	≥150 mg/dL		
High density lipoprotein (HDL) cholesterol			
Men	<40 mg/dL		
Women	<50 mg/dL		
Blood pressure	≥130/≥85 mmHg		
Fasting glucose	≥110 mg/dL		

- 6. Fasting blood glucose >60 mg/dL at screening
- 7. Willingness to allow sample storage for future research
- 8. Able to provide informed consent

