6.1 Screening

The following procedures will be performed at the NIH Clinical Center to determine if a subject is eligible for study participation and are expected to be completed over 2 visits:

- 1. History and physical exam and vital signs including measurement of blood pressure, height, and weight
- Blood collection for laboratory assessments including acute care, hepatic, and mineral panels, Hgb A1c, fasting glucose and insulin, fasting lipid profile, complete blood counts, CRP, HIV viral load, CD4+ T-cell count, and hepatitis serologies
- 3. Urine studies including urinalysis, urine protein/creatinine ratio and albumin/creatinine ratio, and urine drug screen
- 4. Blood or urine pregnancy testing for women of childbearing potential
- 5. Nutrition consultation for body composition measurements including weight, and waist and hip circumference. Subjects will also receive instructions on completion of 3-day food diary.
- 6. Receive a pedometer and instruction on its use to assess daily activity level
- 7. 1-day trial of the very low-calorie diet (approximately 25% of estimated needs) to assess ability and motivation to lose weight through ICR

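### The CD4 eligibility limit in section 4.2 is given per mL while section 1.1.1 counts CD4 per mm³; taken literally, its number screens out almost nobody

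*Combined protocol and SAP*

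**What the plan says.** Section 4.2 (Subject Inclusion Criteria), item 3, sets the CD4 limit: "CD4 >200 cells/mL and no active opportunistic infection or malignancy". The item directly above it sets the virological limit, also per mL and with the same number: "HIV RNA level ≤200 copies/mL for ≥1 year".

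The only other CD4 count with a unit is in section 1.1.1, where an earlier clinic cohort with advanced HIV/AIDS is described by "cluster of differentiation 4 [CD4] < 100 cell/mm³".

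Section 6.1 (Screening) orders the test without a unit: "HIV viral load, CD4+ T-cell count, and hepatitis serologies". The exclusion criteria in section 4.3 contain no CD4 limit, and the visit lists in sections 6.4 and 6.5 do not name a repeat CD4 count. No other section states a CD4 limit or corrects the unit.

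**The concern.** Criterion 3 is an operative rule: it decides who may be randomized, and it holds the only numeric CD4 limit in the protocol. The two sections express CD4 in units that differ by a factor of 1000. If the per-mL unit is applied as written, the number has no screening function, and people in the range that the protocol itself calls advanced disease would satisfy it.

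Two things are at stake. One is agreement between the written rule and the rule that site staff are likely to apply. The other is a clear description of the enrolled population's immune status, which has some relevance because markers of immune activation are among the secondary endpoints in section 3.1.1.2.

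**Working it through.** The plan gives no calculated figure to reproduce here. The check is a unit conversion.

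**Inputs**
- Written limit: 200 cells/mL (section 4.2, item 3).
- Comparison level: 100 cells/mm³ (section 1.1.1).
- Identity: 1 mL = 1 cm³ = 1000 mm³.

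**Steps**
1. Written limit in the unit of section 1.1.1: 200 / 1000 = 0.2 cells/mm³.
2. The same number read per mm³, expressed per mL: 200 × 1000 = 200,000 cells/mL. Ratio of the two readings: 200,000 / 200 = 1000.
3. Smallest non-zero whole count: 1 cell/mm³ = 1,000 cells/mL, which exceeds 200 cells/mL. Among whole-number counts per mm³, only zero fails.
4. Advanced-disease level of section 1.1.1: 100 × 1000 = 100,000 cells/mL, and 100,000 / 200 = 500 times the written limit.

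**Who is affected by the choice of unit**

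| CD4 count (cells/mm³) | Meets the limit read per mL (as written) | Meets the limit if 200 is read per mm³ |
|---|---|---|
| 0.2 or below | no | no |
| above 0.2, up to and including 200 | yes | no |
| above 200 | yes | yes |

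The two readings disagree only in the middle row. For example, a candidate at 150 cells/mm³ has 150,000 cells/mL, so meets the written number but would be refused if 200 were applied per mm³.

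**The case against.** The strongest objection is that there may be no error at all. The text checked was read from PDF by a program, and a micro sign taken for the letter m would turn µL into mL. Cells/µL and cells/mm³ are the same unit, so the discrepancy would vanish. Other special characters came through (α and β in section 1.1.2, ³ in section 1.1.1, ≥ and ² in section 4.2), which weighs against a misreading. But no micro sign appears anywhere in the text, so nothing shows how one would have been read. The per-mL unit in the line above makes an author's slip equally plausible. This objection stands until the source page is checked.

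Second, other limits on immune and infection status remain. Criterion 3 also bars active opportunistic infection and malignancy, criterion 2 requires sustained virological suppression, and section 4.3 lets the investigator exclude anyone whose condition threatens safe participation. This also stands. A reader might infer that the criterion excludes no one, or that it is the only safeguard on immune status. The documents support neither: the point concerns the CD4 number alone. These other limits do not replace a count limit, because none of them sets a CD4 value.

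Third, a reader might infer that if staff apply 200 per mm³, every enrolment departs from the written criterion and cannot be audited against it. That is false. Anyone above 200 cells/mm³ has more than 200,000 cells/mL, so satisfies the written limit and can be audited against it.

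Fourth, calling the limit 1000-fold too low presumes that 200 was meant per mm³. The documents do not say so, and the per-mm³ unit rests on one background sentence about a different cohort. The inference is reasonable, since 0.2 cells/mm³ screens almost nobody, but it remains an inference.

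**Conclusion.** The concern holds in a limited form. As the text stands, "CD4 >200 cells/mL" does not fit the unit in section 1.1.1. Read literally it equals 0.2 cells/mm³, and the CD4 number then screens out essentially nobody. The conversion factor of 1000 is exact. The practical effect is confined to candidates above 0.2 and up to 200 cells/mm³, whom the written number admits and whom staff would probably refuse. The documents give no count of such candidates.

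This rests on two assumptions: that the source page prints mL rather than µL, and that the limit was meant to do some screening.

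It is a unit error in a decision threshold: wrong as written, but with low practical impact, because staff would probably recognise the intended unit. The sample size and power statements in section 12.3 and the analyses in section 12.4 do not use the CD4 limit and are unaffected.

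**What to change.** Check the unit in criterion 3 on the source page. If it reads µL, nothing needs to change.

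If it reads mL, reconcile section 4.2 with section 1.1.1, have the sponsor confirm the intended limit, and state it in the unit in which the screening laboratory reports the count. Section 6.1 gives no unit, so this has to be confirmed with the laboratory. No value is proposed here.

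The cost is one confirmation from the sponsor and a correction to one unit. No calculation, endpoint or analysis has to be redone. If subjects have already been enrolled, their screening counts can be compared with the confirmed limit; only those at or below 200 cells/mm³ could be affected by the choice between the two units.
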